## 5. ANALYSIS POPULATIONS

Data will be summarized using the following analysis populations.

- All Enrolled Subjects: This analysis population will include all enrolled subjects, regardless of whether they received any amount of study drug. The all enrolled subjects population will be used for the summarization of subject disposition.
- Safety Population: This analysis population will include all enrolled subjects who have received any dose of study drug. The safety population will be used for the analysis of safety measures.
- Efficacy Population: This analysis population will include all enrolled patients who have received at least one dose of the study drug and who do not have EGFR or ALK mutant tumors.
- Primary Efficacy Population: This analysis population will include all efficacy population subjects, excluding patients who have not received surgery after neoadjuvant treatment with Atezolizumab, and excluding subjects who have not had a complete resection. This population will be used for primary efficacy analysis. For the primary efficacy population, if major pathological response is unable to be assessed, then it will remain undetermined and the subject will be removed from this population.

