### 6.3.3 Exploratory Analysis

Overall survival (OS) will be analyzed in efficacy population. OS is defined as the time from the date of first dose until the date of death from any cause. This is the length of time from the start of treatment that patients are still alive. Subjects alive at the end of the study or lost to follow-up will be censored on the date of last follow-up disease assessment.

Disease-free survival (DFS) will be analyzed in primary efficacy population. DFS is defined as the time from the first date of no disease (i.e., date of surgery with complete resection) to local or distant recurrence or death due to any cause, whichever occurs first. DFS will be analyzed only for patients who underwent surgery with complete resection. After surgery with complete resection, data for patients who withdraw from the study without disease recurrence or death will be censored at the date of last disease follow-up assessment. Patients without post-surgery disease follow-up assessments but known to be alive will be censored at the date of surgery with complete resection plus one day.

Event-free survival (EFS) will be analyzed in efficacy population. EFS is defined as the time from the date of first dose to any of the following events, whichever occurs first:

- Progression of disease per RECIST v1.1 that precludes surgery with complete resection
- Local or distant disease recurrence
- Death due to any cause

Patients who have not experienced disease progression that precludes surgery with complete resection, local or distant disease recurrence, or death at the time of analysis will be censored at the time of last tumor or disease follow-up assessment. Patients with no post-baseline tumor or disease follow-up assessment but known to be alive will be censored at the date of first dose plus one day.

The durations of overall survival, disease-free survival and event-free survival will be computed in months as:

$$\frac{(End\ Date - Start\ Date + 1)}{(365.25/12)}$$

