The overall survival, disease-free survival and event-free survival will be analyzed using the Kaplan-Meier method for the efficacy population. To describe overall survival, the survival rate, death rate, and overall median, 95% CI, 25th and 75th percentiles, and range will be reported. Furthermore, the patients remaining alive, survival rate, and 95% CI will be reported every 6 months (at 6, 12, 18, 24, 30, and 36 months). To describe disease-free survival and event-free survival, the disease-free rate, not disease-free rate, counts of patients by contributing events, and overall median, 95% CI, 25th and 75th percentiles, and range will be reported. Furthermore, the patients remaining disease-free, disease-free rate, and 95% CI will be reported every 6 months (at 6, 12, 18, 24, 30, and 36 months).

These analyses will also be repeated for each subgroup of major pathologic responder and non-responder, and by subgroups of PD-L1 negative (TC0IC0) and positive (TC123IC123). Subgroups will be compared using a log-rank test.

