	Table 14.1.10.2	Study Drug Exposure, Surveillance/Survival Follow-up Phase	Safety Population
S, P	Table 14.1.11.1	Prior Medications	Safety Population
S, P	Table 14.1.11.2	Concomitant Medications, Neoadjuvant Atezolizumab Therapy Phase	Safety Population
	Table 14.1.11.3	Concomitant Medications, Surveillance/Survival Follow-up Phase	Safety Population
E, P	Table 14.2.1	Primary Efficacy Analysis for Major Pathologic Response Rate	Primary Efficacy Population
E, P	Table 14.2.2.1	Major Pathologic Response Rate within PD-L1 Group	Efficacy Population
E, P	Table 14.2.2.2	Investigator-assessed Response Rate within PD-L1 Group	Efficacy Population
E, P	Table 14.2.3.1	Survival Analysis for Overall Survival (OS)	Efficacy Population

Interim Analysis Flag	Output Type and Number	Output Title	Output Population
E, P	Table 14.2.3.2	Survival Analysis for Disease-Free Survival (DFS)	Primary Efficacy Population
E, P	Table 14.2.3.3	Survival Analysis for Event-Free Survival (EFS)	Efficacy Population
E, P	Table 14.2.3.4	Survival Analysis for Overall Survival (OS)	Efficacy Population
E, P	Table 14.2.3.5	Survival Analysis for Disease-Free Survival (DFS) by Major Pathologic Responder (MPR)	Primary Efficacy Population
E, P	Table 14.2.3.6	Survival Analysis for Event-Free Survival (EFS) by Major Pathologic Responder (MPR)	Efficacy Population
E, P	Table 14.2.3.7	Survival Analysis for Overall Survival (OS) by PD-L1 Group	Efficacy Population
E, P	Table 14.2.3.8	Survival Analysis for Disease-Free Survival (DFS) by PD-L1 Group	Primary Efficacy Population
E, P	Table 14.2.3.9	Survival Analysis for Event-Free Survival (EFS) by PD-L1 Group	Efficacy Population
S, E, P	Table 14.3.1.1.1	Overview of Adverse Events by Highest NCI CTCAE Grade, Neoadjuvant Atezolizumab Therapy Phase	Safety Population
	Table 14.3.1.1.2	Overview of Adverse Events by Highest NCI CTCAE Grade, Surveillance/Survival Follow-up Phase	Safety Population
S, E, P	Table 14.3.1.2.1	Adverse Events by Highest NCI CTCAE Grade, Neoadjuvant Atezolizumab Therapy Phase	Safety Population
	Table 14.3.1.2.2	Adverse Events by Highest NCI CTCAE Grade, Surveillance/Survival Follow-up Phase	Safety Population
S, E, P	Table 14.3.1.2a	Adverse Events by Highest NCI CTCAE Grade, Both Study Phases	Safety Population
S, E, P	Table 14.3.1.2b	Adverse Events With Onset Prior to Date of Surgery by Highest NCI CTCAE Grade, Neoadjuvant Atezolizumab Therapy Phase	Safety Population

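### OS and EFS by pathologic response are run in a population that includes never-resected patients, whose response class is not stated; if they count as non-responders, the EFS comparison favours responders with no true effect

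*SAP*

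**What the plan says.** On OS, SAP 6.3.3 states "Overall survival (OS) will be analyzed in efficacy population" and "OS is defined as the time from the date of first dose until the date of death from any cause". On EFS it states "EFS is defined as the time from the date of first dose to any of the following events", and the first event listed is "Progression of disease per RECIST v1.1 that precludes surgery with complete resection". EFS also uses the efficacy population.

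SAP Section 5 defines that population as enrolled patients "who have received at least one dose of the study drug and who do not have EGFR or ALK mutant tumors". Surgery is not a condition. Only the primary efficacy population is restricted, "excluding patients who have not received surgery after neoadjuvant treatment with Atezolizumab" and also excluding incomplete resections. The rule that an unassessable response stays undetermined and the patient is removed is written for that population alone.

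SAP 6.3.3 then says "These analyses will also be repeated for each subgroup of major pathologic responder and non-responder" and compares the subgroups by log-rank. Table 3 of SAP Section 7 assigns the efficacy population to EFS by response (Table 14.2.3.6, Figure 1.2.6) and to OS by response (Figure 1.2.4). Table 14.2.3.4 has the same population and, by its place in the list, is the matching OS table, although its title omits the subgroup. DFS by response (Table 14.2.3.5, Figure 1.2.5) uses the primary efficacy population, with the clock from surgery.

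Protocol 6.4.3 likewise plans Kaplan-Meier analyses of the efficacy population for responders and non-responders. Neither document specifies a landmark or a time-dependent covariate.

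**The concern.** Response is scored on the resected specimen, and the schedule of activities puts surgery at Day 40 ± 10. Protocol 3.1.2 says that patients with radiologic progression before the second dose have no study resection. If such patients sit in the non-responder group, it receives a block of EFS events in the first weeks that the responder group cannot have. The log-rank test then partly measures whether a patient reached surgery, and a reader would take the result as evidence that pathologic response predicts outcome.

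The by-response tables are flagged for both the efficacy interim and the primary analysis. The paper cited for the response definition proposes it, by its title in the reference list, as a surrogate endpoint. A planned comparison whose false positives point almost entirely one way would be weak support for that idea.

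**Working it through.** The plan gives no event count, power or significance level for this comparison, so there is no planned figure to reproduce. The check asks how often a two-sided 5% log-rank test rejects when response has no effect among resected patients.

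**From the documents.** About 180 enrolled; response rate 15% (the design alternative); surgery at Day 40 ± 10; follow-up read to 36 months.

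**Assumed.** 170 in the efficacy population; unresected share 5–20%; response rate 20% as a second case; exponential times with median EFS 48 months and median OS 84 months after surgery; unresected patients classed as non-responders.

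**EFS by hand: 10% unresected, all progressing before surgery, response rate 15%.**

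- Unresected: 0.10 × 170 = 17. Resected: 153. Responders: 0.15 × 153 = 23.
- Responder share at risk at the early events: 23/170 = 0.135. Expected responder events among the 17: 17 × 0.135 = 2.3. Observed: 0.
- Follow-up after surgery: 36 − 40/30.4 = 34.7 months. Later events: 153 × (1 − 2^(−34.7/48)) = 153 × 0.394 = 60.
- Log-rank variance: 60 × 0.15 × 0.85 + 17 × 0.135 × 0.865 = 7.7 + 2.0 = 9.7.
- Mean z = −2.3/√9.7 = −0.74. Only the later events vary by chance, so the SD of z is √(7.7/9.7) = 0.89.
- P(z < −1.96) = Φ((−1.96 + 0.74)/0.89) = Φ(−1.37) = 8.5%.

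Simulation of the same case gives mean z −0.72 and 8.4% rejection, of which 8.2 points favour responders.

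**Simulated two-sided rejection, no true effect** (2,000 or more runs per case; Monte Carlo standard error about 0.5 points at 5%):

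| Unresected share (assumed) | 5% | 10% | 15% | 20% |
|---|---|---|---|---|
| EFS, all progress before surgery, response 15% | 5.6% | 8.4% | 15.8% | 21.9% |
| Same, response 20% | 6.2% | 12.1% | 21.2% | 34.5% |
| EFS, half progress, other half median 24 months, response 15–20% | not run | 5–9% | 8–12% | 12–17% |
| EFS, half progress, other half median 48 months, response 15–20% | 4–5% | 5–6% | 6–8% | 8–10% |
| OS, unresected median 84 months (as resected), response 15% | 4.8% | 5.1% | 5.1% | 4.3% |
| OS, unresected median 24 months, response 15–20% | 4–5% | 5–6% | 6–10% | 9–13% |

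**OS, lead-in alone.** With one hazard for everyone (median 84 months), 1 − 2^(−1.3/84) = 1.1% die before Day 40. That is about 1.8 of 170 patients, with 1.8 × 0.15 = 0.27 responder deaths expected and none possible. By 36 months there are 170 × (1 − 2^(−36/84)) = 44 deaths, so the log-rank SD is √(44 × 0.15 × 0.85) = 2.4 and the shift in z is about −0.27/2.4 = −0.11. Simulated rejection is 4.0%.

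**With unresected patients left out.** Rejection is 4.3–6.2% with the clock from surgery and 4.3–6.1% with the clock still at first dose. Both groups then share the same event-free lead-in, so the restriction does nearly all the work and the start date little.

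**The case against.** The strongest objection is that the SAP never says unresected patients are non-responders. Where it wants unevaluable patients counted as failures it says so: SAP 6.3.2 does this for RECIST response and not for pathologic response. If patients without a specimen have no response status and drop out, there is no bias even from first dose. This stands, and it makes the point conditional. It does not remove it, because the listed population includes these patients, only two groups exist, and the removal rule does not reach this population.

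A reader might infer that guaranteed event-free time biases both endpoints. The documents do not support that for OS: over 36 months the lead-in is negligible, and the OS figures above come from an assumed difference in prognosis. A reader might also infer that the EFS inflation is certain. It depends on the unresected share and on how many of those patients progress; neither is given, and patients unresected for other reasons have no immediate EFS event.

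Three further points stand. DFS by response is already planned in completely resected patients from surgery and, as SAP 6.3.3 defines it, is unaffected. The comparison is exploratory, with no decision attached. Testing pathologic response as a surrogate is not a stated objective, so how readers will use the result is a judgement.

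**Conclusion.** The point holds conditionally. The plan leaves open the response class of unresected patients in OS and EFS by response, and its plainest reading counts them as non-responders. On that reading the EFS test is biased toward responders: about 8–12%, 16–21% and 22–35% rejection at 10%, 15% and 20% unresected if all progress before surgery. If half do and the rest also fare worse than resected patients, it is about 5–9%, 8–12% and 12–17%. At 5% unresected it stays close to 5%.

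OS is affected only if unresected patients survive less well: about 5–6%, 6–10% and 9–13% with medians of 24 against 84 months. The unresected share, the progressing fraction and all medians are assumptions. The correction is worth making before the outputs are produced, but no trial conclusion on the primary endpoint depends on it.

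**What to change.** In SAP 6.3.3 and Table 3, run OS and EFS by response (Tables 14.2.3.4 and 14.2.3.6, Figures 1.2.4 and 1.2.6) in the primary efficacy population, that is, patients with complete resection and a determined response. Preferably start the clock at surgery as the landmark. State that unresected, incompletely resected and unassessable patients are not counted as non-responders in these comparisons. Keep OS and EFS from first dose in the efficacy population for the overall curves, and add the subgroup to the title of Table 14.2.3.4.

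The cost is a few sentences, a population filter and a start date in four outputs. Unresected patients leave only the by-response comparisons. The downside is that EFS by response from surgery comes close to the planned DFS by response. If the sponsor wants to keep the first-dose origin there, the population restriction alone removes the bias.

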#### 6.4 Safety Analysis

##### 6.4.1 Adverse Events (AE)

All reported adverse events terms will be coded to a system organ class (SOC) and preferred term (PT) using the Medical Dictionary for Regulatory Activities version 19.1 or higher if available.

Treatment related adverse events are those adverse events flagged as suspected to be caused by Atezolizumab.

##### Neoadjuvant Atezolizumab Therapy Phase

For the Neoadjuvant Atezolizumab Therapy Phase of the study, an adverse event will be any event that starts following the start of the first dose of study drug for those subjects not continuing in the Surveillance/Survival Follow-up Phase of the study, and through the day immediately preceding the start date of the first adjuvant cycle for subjects continuing in the Surveillance/Survival Follow-up Phase of the study.

---

If the onset date and/or resolution date of an adverse event is incomplete (for example, only the month and year are available), the event will be assumed to start after the first dose of study drug, as long as the available information does not conclusively indicate that the event emerged prior to the start date of the first cycle of study drug administration.

An overview of adverse events will present the number and percentage of safety population subjects who have at least one AE, at least one Grade 3 or higher AE, at least one treatment related AE, at least one serious AE, at least one AE of special interest, at least one AE leading to study drug withdrawal, at least one AE leading to death, and at least one treatment related AE leading to death, overall (subjects counted only once if any AE is experienced) and by highest NCI CTCAE grade (subjects counted only once at the highest grade level experienced).

The number and percentage of safety population subjects with AEs will be summarized by SOC and PT in total, and by highest NCI CTCAE grade. At each summary level, a subject will be counted only once if he/she experiences at least one AE, and when summarizing by highest NCI CTCAE grade, a subject will be counted only once at the highest grade level experienced. AE summary tables will be sorted by descending occurrence rate according to the SOC, and then by descending occurrence rate within PT. The following types of AE summaries will be prepared:

- All AE
- Grade  $\geq 3$  AE
- Onset date prior to date of surgery (Neoadjuvant Atezolizumab Therapy Phase only)
- Onset date on or after date of surgery, for safety population with surgery date (Neoadjuvant Atezolizumab Therapy Phase only)
- Treatment related AE
- Serious AE
- AE of special interest
- AE leading to death
- Treatment related AE leading to death
- AEs leading to study drug withdrawal

All adverse events will be listed including the AEs which start before the first dose of study drug, and additional separate listings will be created for AEs leading to death, serious AEs, and AEs leading to study drug withdrawal.

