3.1.4 Adjuvant Atezolizumab Therapy Phase

Patients whose tumors have evidence of pathologic response or lack of radiographic progression will be eligible for the Adjuvant Atezolizumab Therapy Phase, which will occur during the Surveillance period.

During this part of the study, patients will receive adjuvant atezolizumab for up to a maximum of 12 additional months (up to 18 cycles). Adjuvant atezolizumab treatment may be started directly after surgery or after adjuvant SOC chemotherapy (with or without radiation). Choice of adjuvant SOC chemotherapy will be at the discretion of the treating physician, depending on the disease stage, as deemed clinically appropriate. It is highly recommended that any adjuvant treatment be initiated within 120 days after surgery. Additionally, it is recommended that patients who receive SOC Chemotherapy (\pm Radiotherapy) initiate adjuvant atezolizumab within 60 days of SOC Chemotherapy \pm Radiotherapy (whichever occurs last). If adjuvant treatment is planned to start outside of the recommended window, *Investigators may discuss it with the Medical Monitor.*

Whole blood samples will be collected prior to infusion on adjuvant Cycle 1, Day 1. Subsequent blood samples will be collected during Surveillance (see Section 3.1.3) and 30 days after the last dose for correlative studies. The blood will be processed for PBMC, plasma, and serum.

Optional bronchial brushings samples may be collected from patients undergoing bronchoscopy or EBUS at prescreening or screening and approximately 3–4 months after starting adjuvant atezolizumab treatment (Group D only).

For all patients whose disease progresses or recurs (confirmed by imaging) at any time between neoadjuvant treatment and surveillance may undergo an optional tissue biopsy (tumor and lymph node, if available) for correlative studies, which will require a separate ICF signature (see Section 4.5.1). A blood sample will also be collected at the time of disease progression/recurrence.

All patients will enter Survival Follow-up, which will cover new anti-cancer treatment, DFS, and OS for up to 3 years after the last dose of atezolizumab (See [Appendix 2](#) for details regarding time in Survival Follow-up).

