5.3.1 Adverse Event Reporting Period

Investigators will seek information on adverse events at each patient contact. All adverse events, (including the neoadjuvant phase, surgery phase, and adjuvant phase) whether reported by the patient or noted by study personnel, will be recorded in the patient's medical record and on the Adverse Event eCRF.

After informed consent has been obtained **but prior to initiation of study drug**, only serious adverse events caused by a protocol-mandated intervention (e.g., invasive procedures such as biopsies, discontinuation of medications) should be reported (see Section [5.4.2](#) for instructions for reporting serious adverse events).

After initiation of study drug, all adverse events will be reported until 30 days after the last dose of atezolizumab (neoadjuvant or adjuvant, whichever occurs last). Serious adverse events and non-serious adverse events of special interest will be reported until 90 days after the last dose of atezolizumab (neoadjuvant or adjuvant, whichever occurs last). For patients participating in the Adjuvant Atezolizumab Therapy Phase, as outlined in Section [3.1.4](#), who will receive and complete SOC chemotherapy prior to adjuvant atezolizumab, all AE's will be reported from their first dose of neoadjuvant atezolizumab until 30 days after the last dose of adjuvant atezolizumab. Additionally, serious adverse events and non-serious adverse events of special interest will be reported until 90 days after the last dose of adjuvant atezolizumab for these patients. During the Surveillance Period, as outlined in Section [3.1.3](#), if a patient is not receiving atezolizumab, only serious adverse events associated with CT scans, blood sample collection, and the optional biopsy (collected at the time of disease progression) will be collected and reported (see [Table 5](#)).

Table 5 Reporting Requirements After Initiation of Study Drug (by Treatment Subgroup)

Safety Reporting Requirements	Subgroup A	Subgroup B	Subgroup C	Subgroup D
No Adjuvant Treatment	Adjuvant Atezolizumab Treatment	SOC Chemotherapy (± Radiotherapy) only	SOC Chemotherapy (± Radiotherapy) plus Adjuvant Atezolizumab	

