AEs	From first dose of neoadjuvant atezolizumab until 30 days after last dose of neoadjuvant atezolizumab ^b	From first dose of neoadjuvant atezolizumab until 30 days after last dose of adjuvant atezolizumab ^{a, b}	From first dose of neoadjuvant atezolizumab until 30 days after last dose of neoadjuvant atezolizumab ^b	From first dose of Neoadjuvant atezolizumab until 30 days after last dose of Adjuvant atezolizumab ^{a, b}
SAEs/AESIs	From first dose of neoadjuvant atezolizumab until 90 days after last dose of neoadjuvant atezolizumab ^{b, c}	From first dose of neoadjuvant atezolizumab until 90 days after last dose of adjuvant atezolizumab ^{a, b, c}	From first dose of neoadjuvant atezolizumab until 90 days after last dose of neoadjuvant atezolizumab ^{b, c}	From first dose of neoadjuvant atezolizumab until 90 days after last dose of adjuvant atezolizumab ^{a, b, c}

AE = adverse event; AESI = adverse event of special interest; SAE = serious adverse event;

SOC = standard of care.

- ^a No safety reporting interruption between neoadjuvant and adjuvant atezolizumab.
- ^b After informed consent has been obtained but prior to initiation of study drug, adverse events should be reported as outlined in Section 5.3.1. During Surveillance, but after patients have already completed atezolizumab treatment, AEs should be reported as outlined in Section 5.3.1.
- ^c Serious adverse events associated with CT scans, blood sample collection, and the optional biopsy (collected at the time of disease progression) will be collected and reported during the entire Surveillance period.

Instructions for reporting adverse events that occur after the adverse event reporting period are provided in Section 5.6.

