Patients who undergo surgery and receive adjuvant atezolizumab therapy will enter the Adjuvant Atezolizumab Therapy Phase. The Adjuvant Atezolizumab Therapy Phase is exploratory and will evaluate atezolizumab adjuvant therapy for up to a maximum of 12 months (up to 18 cycles) in patients who demonstrate clinical benefit (evidence of pathologic response or absence of radiographic progression) from the Neoadjuvant Atezolizumab Therapy Phase. After surgical resection, patients may receive SOC adjuvant chemotherapy (with or without radiation) before starting atezolizumab adjuvant therapy. Any adjuvant treatment (optional SOC chemotherapy  $\pm$  radiotherapy and/or adjuvant atezolizumab) will be done concomitantly with Surveillance.

For clarity of assessments during the Surveillance period, patients will be grouped by adjuvant treatment and overall:

- Subgroup A: No Adjuvant Treatment
- Subgroup B: Adjuvant Atezolizumab Treatment
- Subgroup C: SOC Chemotherapy ( $\pm$  Radiotherapy) Only
- Subgroup D: SOC Chemotherapy ( $\pm$  Radiotherapy) + Adjuvant Atezolizumab Treatment

Neoadjuvant treatment (Neoadjuvant Atezolizumab Therapy Phase) with atezolizumab 1200 mg every 21 days (one cycle = 21 days) will be given for a maximum of 2 cycles, and adjuvant treatment (Surveillance/Survival Follow-up Phase) with atezolizumab 1200 mg every 21 days will be given for a maximum of 12 months.

Patients could be asked to consent to an optional prescreening tumor biopsy, which will then be used for tissue analysis if the patient is eligible to participate in the study based on pathologically documented NSCLC and other eligibility criteria. This prescreening consent form also includes optional collection of bronchial brushing samples and lymph node samples.

Additionally, patients whose disease progresses or recurs anytime between the neoadjuvant phase and end of surveillance period will be asked to consent to an optional tissue biopsy (tumor and

---

lymph node, if available) at the time of progression/recurrence. Images will be collected at the time of progression and reviewed.

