## 4. SCHEDULE OF ASSESSMENTS

Assessment	Part 1 – Atezolizumab Neoadjuvant Treatment				Surgery			Neo- adjuvant Atezo Treatment Completo n/ D/C d	Surveillance			Disease Progres sion or Recurre nce g	Survival Follow- up h	
					Pre- surgery b		Surgery		All Subgroups	For Subgroups B and D only				
	Day -42 to -1	Day -14 to -1	C1D1 (Day 22 ±3) i	C2D1 (Day 22 ±3) j	Day 36 (±3)	Day 40 (±10) j	30 (± 5) days after surgery		Every 6 weeks to 3 months for up to 2 years k	Adjuvant Atezo Treatment e,f	Adjuvant Atezo Treatment c,f	Adjuvant Atezo Treatment Completion / D/C d		
(Window [Days])	Day -42 to -1	Day -14 to -1	C1D1 (Day 22 ±3) i	C2D1 (Day 22 ±3) j	Day 36 (±3)	Day 40 (±10) j	4–6 weeks after surgery	30 (± 5) days after last dose	Every 6 weeks to 3 months for up to 2 years k	Adjuvant Cycle 1, Day 1, (±5) days	Adjuvant Cycle 2–17, Day 1 (±5) days i	30 (± 5) days after last dose	30 days after progressio n/ recurrence (± 5) days j	Up to 3 years
Informed consent (prescreening ICF and main ICF) m	x													
Prescreening biopsy									See footnote n					
Medical history and demographic data o	x													
Weight	x								x	x				
Height	x													
Complete physical examination p	x				x q									

Assessment	Part 1 – Atezolizumab Neoadjuvant Treatment				Surgery			Neo- adjuvant Atezo Treatment Completi- on/ D/C d	Surveillance				Disease Progres- sion or Recurren- ce g	Survival Follow- up h
									All Subgroups		For Subgroups B and D only			
	Surveillanc- e for All Treatment Subgroups See Appendix 2	Adjuvant Atezo Treatment e, f	Adjuvant Atezo Treatment c, f	Adjuvant Atezo Treatment Completion / D/C d										
(Window [Days])	Day -42 to -1	Day -14 to -1	C1D1 (Day 1±3) i	C2D1 (Day 22 ±3) i	Day 36 (±3)	Day 40 (±10) i	4–6 weeks after surgery	30 (± 5) days after last dose	Every 6 weeks to 3 months for up to 2 years k	Adjuvant Cycle 1, Day 1, (±5) days	Adjuvant Cycle 2–17, Day 1 (±5) days i	30 (± 5) days after last dose	30 days after progressio- n/ recurrence (± 5) days i	Up to 3 years
Limited physical examination r					X			X		X	X s	X		

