#### 6.5.1 Planned Interim Analysis

##### 6.5.1.1 *Planned Interim Safety Analysis*

After the first 30 patients complete protocol-specified atezolizumab treatment and undergo the planned surgical resection of their tumor, all safety population subjects at that time will be evaluated for tolerability and safety of the neoadjuvant regimen. If, at the time of the safety interim analysis, three or more patients have experienced Grade 5 adverse events related to protocol treatment, then the study may be discontinued.

Outputs from this SAP which will facilitate the planned interim safety analysis are flagged in Section 9 of this SAP.

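### The SAP's neoadjuvant adverse-event window stays open through Subgroup D's postoperative chemotherapy and radiotherapy, so their toxicity enters the all-cause neoadjuvant tables

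*SAP*

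**What the plan says.** SAP 6.4.1 defines the neoadjuvant-phase window. It opens at the first dose of study drug and, for patients who go on, runs "through the day immediately preceding the start date of the first adjuvant cycle for subjects continuing in the Surveillance/Survival Follow-up Phase of the study". The SAP does not define the first adjuvant cycle. In the schedule in SAP Section 4, "Adjuvant Cycle 1, Day 1" heads a column of adjuvant atezolizumab treatment, for Subgroups B and D only. SAP 3.1 attaches the later phase's name to the same drug: "adjuvant treatment (Surveillance/Survival Follow-up Phase) with atezolizumab 1200 mg every 21 days".

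SAP 3.1 also gives the order of treatment: "After surgical resection, patients may receive SOC adjuvant chemotherapy (with or without radiation) before starting atezolizumab adjuvant therapy". Patients who have both form Subgroup D. For them Protocol 5.3.1 states that "all AE's will be reported from their first dose of neoadjuvant atezolizumab until 30 days after the last dose of adjuvant atezolizumab", and a footnote to Protocol Table 5 adds "No safety reporting interruption between neoadjuvant and adjuvant atezolizumab".

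For the later phase, SAP 6.4.1 opens the window at the first dose of study drug, not at the first adjuvant dose.

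**The concern.** Safety as neoadjuvant treatment is a stated objective, separate from safety as adjuvant treatment. A reader will take a table titled for the Neoadjuvant Atezolizumab Therapy Phase to describe two doses of atezolizumab and the operation that follows. In Subgroup D the window also takes in a course of chemotherapy, sometimes with radiotherapy, and every adverse event during it is collected. Nothing in the SAP closes the window, or flags events, when other anticancer therapy starts.

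This is a problem of attribution to a treatment period, not only of unequal follow-up. Chemotherapy events would be labelled neoadjuvant even if every patient were followed for the same time. The on/after-surgery tables matter most here, because Protocol 6.7.1.1 names resection after checkpoint inhibitors as the area where safety data are sparse.

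**Working it through.** The plan states no figure for this point, so there is none to reproduce. The check compares the definitions and then counts days.

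**Step 1: which tables take in the events.** Under SAP 6.4.1 and SAP Table 3:
- Affected: the whole-phase all-cause tables, namely overview (14.3.1.1.1), all AEs (14.3.1.2.1), Grade ≥3 (14.3.1.3.1), serious (14.3.1.5.1) and special interest (14.3.1.6.1); and the on/after-surgery tables 14.3.1.2c and 14.3.1.5c.
- Not affected: the before-surgery tables 14.3.1.2b, 14.3.1.4a and 14.3.1.5b.
- Affected only through attribution: the treatment-related tables, including 14.3.1.4b, which require suspected causation by atezolizumab.
- Counted again: the later-phase window opens at the first dose of study drug, so the same events also enter the Surveillance/Survival Follow-up tables.

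**Step 2: the other subgroups.** Subgroups A and C enter Surveillance but have no adjuvant atezolizumab cycle, so the rule gives them no end date. Protocol 5.3.1 stops their general AE collection 30 days after the last neoadjuvant dose (22 + 30 = Day 52) and collection of serious events and events of special interest at 90 days (22 + 90 = Day 112). Chemotherapy toxicity in Subgroup C therefore enters only in part, through early serious or special-interest events.

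**Step 3: days in the window, Subgroup D.** From the documents:
- second dose on Day 22 and surgery on Day 40 (schedule of activities, nominal days)
- adjuvant treatment recommended within 120 days of surgery, and adjuvant atezolizumab within 60 days of SOC therapy (Protocol 3.1.4)

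Assumed:
- chemotherapy starts no earlier than 42 days after surgery
- four 21-day cycles, so 3 × 21 = 63 days from first to last dose
- a gap of at least 21 days before adjuvant atezolizumab

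Last day of the window = surgery + time to SOC start + 63 + gap − 1:
- shortest: 40 + 42 + 63 + 21 − 1 = Day 165
- longest: 40 + 120 + 63 + 60 − 1 = Day 282

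SOC therapy starts between 40 + 42 = Day 82 and 40 + 120 = Day 160. A cut there removes 63 + 21 = 84 to 63 + 60 = 123 days.

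With a start at 28 to 120 days, a duration of 63 to 126 days and the same gaps, the window ends between 40 + 28 + 63 + 21 − 1 = Day 151 and 40 + 120 + 126 + 60 − 1 = Day 345.

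**Step 4: patients.** Protocol 4.1 expects about 50 of about 180 patients in the adjuvant atezolizumab phase, Subgroups B and D together. Ceiling for Subgroup D: 50/180 = 27.8%. The split between B and D is not given.

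**Step 5: illustration for Grade ≥3 incidence.** Added incidence = (patients in D × Grade ≥3 rate during SOC therapy)/180, if none of them had an earlier Grade ≥3 event. Both inputs are assumed:
- 15 × 0.30/180 = 2.5 percentage points
- 35 × 0.50/180 = 9.7 percentage points

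Allowing for earlier events, with a true rate of 10%, 25 patients in D and a 40% rate during SOC therapy: (18 + 25 × 0.9 × 0.4)/180 = 15.0% reported.

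**The case against.** The strongest reply is that the SAP already supplies clean figures. All AEs, related AEs and serious AEs each have a before-surgery table, and the all-AE one is by highest grade, so a preoperative Grade ≥3 figure can be read from it. That stands. It does not help the whole-phase Grade ≥3 and special-interest tables, which have no listed split, or the on/after-surgery tables.

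A reader might infer that the interim safety look is compromised, because "all safety population subjects at that time will be evaluated for tolerability and safety of the neoadjuvant regimen". The documents do not support that: the stopping criterion in SAP 6.5.1.1 counts Grade 5 events related to protocol treatment, not all-cause incidence. SAP 6.1.2 does set missing causality to related, but Protocol 5.3 and 5.3.4 require the investigator to assess causality for every recorded event, so missing values should be few.

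It is also tempting to say that these events are reported only as neoadjuvant, or that chemotherapy effects dominate the post-surgery tables. The first fails because the later-phase window counts them too. The second has no support: 15 to 35 patients are 8.3% to 19.4% of 180, and everyone in those tables had surgery.

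The term adjuvant cycles is not used consistently either. Protocol Appendix 2 applies it to the chemotherapy-only group. If the SAP meant chemotherapy cycles, the window would close in time. Its own schedule and phase naming point to atezolizumab, and the ambiguity is itself a reason to define the term.

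Finally, the safety analysis is descriptive, and a long window catches late events. Protocol 1.2.2.1 describes a longer time to onset for immune-mediated events. That is a fair reason to keep such events visible, but not to mix them with chemotherapy toxicity under a neoadjuvant title.

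**Conclusion.** The point holds for the all-cause neoadjuvant tables and the on/after-surgery tables. As written, they mix two doses of atezolizumab and surgery with SOC chemotherapy and radiotherapy in Subgroup D.

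The documents do not fix the size. The ceiling of 27.8% rests on the protocol's expected 50 patients and on all of them being in Subgroup D. The 2.5 to 9.7 points depend on assumed patient numbers and toxicity rates and should not be read as an estimate. The window lengths rest on an assumed chemotherapy course, and the 120 days is a recommendation, not a limit, so longer windows are possible. Comparing Day 165–282 with Day 52 would overstate what a cut at SOC start achieves, which is 84 to 123 days on these inputs.

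The SAP should be changed, because a stated objective depends on these tables and the correction is cheap. No hypothesis test is affected.

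**What to change.** In SAP 6.4.1, neoadjuvant phase:
- Define the first adjuvant cycle.
- End the window on the day before the earliest of first SOC chemotherapy, first adjuvant radiotherapy or first adjuvant atezolizumab.
- For patients who receive none of these, end it at the protocol's collection limits: 30 days after the last neoadjuvant dose, and 90 days for serious events and events of special interest.
- Apply the same cut to Tables 14.3.1.2c, 14.3.1.4b and 14.3.1.5c.

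Tabulate the SOC interval separately for all Safety Population patients. Include events of special interest and atezolizumab-related events with onset in that interval, so that delayed immune-mediated events stay visible.

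In SAP 6.4.1, later phase: open the adjuvant window at the first adjuvant atezolizumab dose, which removes the double count.

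The cost is a few SAP sentences, an added table set and some programming. No patient procedure changes. Chemotherapy and radiotherapy are already planned for Listings 16.2.6.12 and 16.2.6.13. Those listings cover the Efficacy Population, so the cut dates must be derived for the whole Safety Population. The downside is that some delayed immune-mediated events move from the neoadjuvant tables to the SOC-interval table.
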